Appendix B1: Morisky Medication Adherence (MMAS) Scale

MMAS-8	Points
Do you sometimes forget to take your pills?	1
People sometimes miss taking their medications for reasons other than forgetting. Thinking over the past two weeks, were there any days when you did not take your medicine?	1
Have you ever cut back or stopped taking your medicine without telling your doctor because you felt worse when you took it?	1
When you travel or leave home, do you sometimes forget to bring along your medicine	1
Did you take all your medicine yesterday?	1
When you feel like your symptoms are under control, do you sometimes stop taking your medicine?	1
Taking medicine every day is a real inconvenience for some people. Do you ever feel hassled about sticking to your treatment plan?	1
How often do you have difficulty remembering to take all of your medicine? A. Never/rarely B. Once in a while C. Sometimes D. Usually E. All the time	0-5

Adherence	MMAS-8 Score
High Adherence	0
Medium Adherence	1-2
Low Adherence	3-8

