Protocol Version 4.0
11May2017

Title:

Once-daily regimen with Envarsus® to optimize immunosuppression management and adherence in kidney transplant recipients

Institution:

Medical University of South Carolina

Principal Investigator:

[name]
Office: [contact]
[contact]
Email: [contact]

Sub-Investigators:

[name]
Office: [contact]
[contact]
Email: [contact]

[name]
Office: [contact]
[contact]

[name] [name]
Office: [contact]
Email: [contact]

1. Study Objectives

1. Primary objective

1. Estimate change from baseline to six months in adherence superiority measure by MMAS-8 in patients converted to a once-daily immunosuppressant regimen of Envarsus[®], everolimus, and prednisone versus patients converted to a twice-daily regimen of Envarsus[®] (once daily), MMF (twice daily), and prednisone (once daily).

2. Secondary objectives

1. Estimate the composite of treatment failure rate, defined as acute allograft rejection with a Banff grade 1A or higher, graft loss, or death at six months post-conversion, in patients converted to a once-daily immunosuppressant regimen of Envarsus[®], everolimus, and prednisone versus patients converted to a twice-daily regimen of Envarsus[®], MMF, and prednisone.

3. Outcomes 3.3.2 through 3.3.11 are considered exploratory

1. Examine subject specific change of the Memphis Medication Side Effect Scale (Appendix B2, 12) at the time of the conversion versus six months post-conversion, compared between the two arms (Appendix B2).
2. Examine subject specific change in quality of life, using the SF-36 (Appendix B3) at the time of conversion versus six months post-conversion, compared between the two arms.
3. Measure and compare time-to-event analysis of secondary objective between the two arms
 1. Patient death (time to event analysis)
 2. Biopsy proven acute rejection (Banff 1a or higher, time to event analysis)
 3. Graft loss (time to event analysis)
4. Examine the medication possession ratio (MPR) of adjunctive immunosuppressants (Everolimus or mycophenolate) during follow up between the two arms
 1. Compare the prevalence of patients with MPR >80%
5. Compare rates of adverse events and severe adverse events between the two arms
6. Perform exploratory analysis of subclinical rejection and IF/TA in patients with one year protocol biopsies as compared to three month protocol biopsies between the two arms

2. Background

1. Rationale

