 1. For the first three months (± 2 months) post-transplant, the pool of patients from which subject of this study will be recruited will receive the current standard of care. Standard of care is described as a regimen of tacrolimus IR BID (5-12ng/mL) + MMF 1g BID + prednisone QD Three months (± 2 months) post-transplant and at the time of recruitment, they are randomized to one of the two arms to either receive a complete once-a-day regimen or to receive twice-daily regimen.
 2. Post-randomization, subjects will be converted to one of the two arms, as shown below, and followed for a total period of six months (primary endpoint), or until a terminal end point is reached.
 1. Arm 1: Control-- twice-daily regimen of Envarsus QD (5 - 12ng/mL) + MMF (goal dose 1g BID) + prednisone QD for 6 months

2. Arm 2: Intervention-- once-a-day regimen of Envarsus QD (2- 5ng/mL) + everolimus QD (3-8ng/mL) + prednisone QD for 6 months
 1. Envarsus will be supplied for both Arms from Veloxis Pharmaceuticals
2. Adherence assessment
 1. Adherence to the study intervention will be assessed at all study visits noted on the Schedule of Evaluations (Section 5.1), using the eight point Morisky Medication Adherence Scale (MMAS-8) (17).
5. Clinical and laboratory evaluations
 1. Schedule of evaluations

Data Collection Schedule

Report Form		Baseline	Days Post-Conversion							
			7±2	14±3	30±5	60±7	90±7	120±7	150±7	180±7
Informed Consent Obtained		X								
Randomization		X								
Review of Inclusion and Exclusion Criteria		X								
Medical History		X								
Kidney Transplant Recipient		X								
Vital Signs		X					X			X
Review of Medications and Dosing		X								
Clinical assessment*	Adverse events, dosage and adherence, rejection, infection, hospitalization				X	X	X	X	X	X
	MMAS-8, MMSE Scale, and SF36 (15,16,20)	X								X
Laboratory Assessments	CBC and Chem-7 ¹	X*	O	O	O	O	O	O	O	X*
	Everolimus CO ₂		X*	X*	X*	X*	X	X*	X*	X*
	Tacrolimus CO ₂	X*	X*	X*	X*	X*	X	X*	X*	X*
End of Study										X

X=required; O=optional: data will be collected if performed as standard of care; *=not current standard of care

Footnotes:

1. Includes sodium, potassium, chloride, CO₂, BUN, SrCr, glucose, calcium, WBC, HgB, Hct, platelets
2. Tacrolimus and Everolimus concentrations will be 12- or 24-hour levels , drawn in the morning of each assessment

2. Timing of evaluation
 1. Pre-Randomization Evaluations
Baseline

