AEs and SAEs will be reported in accordance with the FDA Guidelines for Post-Marketing Reporting of Adverse Events 21 CFR 314.80 and 21 CFR 600.80

<http://www.fda.gov/medwatch/report/regs.htm>. Any serious adverse event or a non-serious adverse event that is related to the study and unexpected will be reported to the FDA, per reporting guidelines, as soon as possible, but no later than 15 working days.. Further, all serious adverse events that are related to the study and are unexpected must be reported to The Medical University of South Carolina IRB within 10 days per The Medical University of South Carolina IRB Unanticipated Problems and Adverse Events Policy and Procedures reporting guidelines.

9. Criteria for intervention discontinuation

1. The intervention will be withheld/discontinued for AE of grade 3 or higher or if requested by the study participant.
2. Additionally, the intervention will be discontinued if the subject meets criteria for the following reasons:
 1. Pregnancy: If a woman becomes pregnant or a male's female partner becomes pregnant while on-study, the subject will be required to instruct investigators immediately.
 2. Loss of graft: Defined as death or need for retransplant. Patients will be deemed a treatment failure and the intervention will be discontinued.\

10. Statistical considerations

1. Outcomes
 1. Primary outcome- Treatment efficacy, defined difference in change from baseline to six month measure by MMAS-8 in both arms.
 2. Secondary objectives
 1. Secondary outcome- Safety outcomes of treatment failure rate, defined as acute allograft rejection with a Banff grade 1A or higher, graft loss, or death at one year post-conversion in both arms.

2. Sample size estimation for the primary outcome

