- 1.** No formal power analysis conducted since this is a pilot study. However, the sample size proposed (n=40) would be able to observe a mean difference between groups in the change of MMAS-8 scores of 2 ± 2 points (95% CI 0.73,3.27) with 87% power. Additionally, a mean difference between groups in the change in the Memphis Side Effect Scale (MSES) of 5 ± 5 points (95% CI 1.83,8.17) would have 87% power in the current sample size. Given the average MSES score of 25 points in kidney transplant patients within 2 years of transplant, this appears to be a feasible outcome (11). In order to demonstrate noninferiority in treatment failure, it would require 400 subjects (200 in each group) to have 80% power, estimating a treatment failure rate of 20% and an acceptable difference of 10%. We expect that 70% of those approached meeting study inclusion/exclusion criteria will agree to participate and that 85% of those that consent and are enrolled in the study will complete all visits. If the 95% CIs for the actual enrollment and completion proportions are outside of these thresholds, then feasibility will not be met. If the 95% CIs encompass these expected values, then feasibility will be met.

3. Missing data and imputation methods

- 1.** Under the intention-to-treat principle, all subjects are included in the analysis. Extensive efforts will be made to keep all missing data to a minimum and minimize loss to follow-up (LTFU). However, it is likely that some missing data may occur.

11. Human subjects

1. Institutional review board (IRB) review and informed consent

- 1.** This protocol, the ICF, and any subsequent modifications must be reviewed and approved by the IRB. A signed and dated ICF must be obtained from the subject as defined in 21CFR50.3. The ICF must also be signed and dated by a member of the study staff qualified to be delegated the authority to obtain informed consent. A copy of the ICF must be given to the subject and the consent process must be documented in the subject's medical record. The PI or delegated sub-Investigator is responsible for ensuring that informed consent is obtained from each patient prior to conducting any study-related activities.

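### Appendix B1, the only scoring key for the primary MMAS-8 change score, contradicts itself: the item points total 12, the category table stops at 8, and item 8's five options have no individual values

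*Combined protocol and SAP*

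**What the plan says.** Section 1 sets the primary objective as "Estimate change from baseline to six months in adherence superiority measure by MMAS-8", and Section 10 (Outcomes) restates it as "Treatment efficacy, defined difference in change from baseline to six month measure by MMAS-8 in both arms". The sample size paragraph in Section 10 plans for a "mean difference between groups in the change of MMAS-8 scores of 2 ± 2 points (95% CI 0.73,3.27) with 87% power". None of these places gives a scoring rule. The Adherence assessment paragraph under Study interventions refers to "using the eight point Morisky Medication Adherence Scale (MMAS-8) (17" and otherwise relies on reference 17.

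That leaves Appendix B1. It has two tables:

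- The points table assigns 1 to each of items 1 to 7. For item 8 it prints "remembering to take all of your medicine? A. Never/rarely B. Once in a while C. Sometimes D. Usually E. All the time 0-5", with no value against any single option.
- The category table sets High Adherence at 0 and Medium at 1 to 2, and finishes with "Low Adherence 3-8".

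**The concern.** The two tables describe different scales. The points table allows totals up to 12, while the category table recognises none above 8. Item 8 also offers five answers for six integer values, so a scorer cannot derive the value of an answer even by taking the points column at face value.

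The primary outcome is a numeric change in this total, so the choice of key sets the range of the score, the weight of item 8 and the meaning of a one-point change. Item 8 asks about difficulty remembering medication. The Rationale names forgetfulness as a leading reason patients give for nonadherence and says the evening dose suffers most. The item with the undefined weight is therefore close to the mechanism the once-daily regimen is meant to act on. The trial is open-label, so a key left open could also be settled after results by arm are visible.

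**Working it through.** **Inputs.** Items 1 to 7 at 1 point each, item 8 at 0 to 5 with options A to E, and a top category ending at 8 (Appendix B1); difference 2 and SD 2 (Section 10, sample size); 20 subjects per arm (Section 3). The significance level is not stated. I assume two-sided 0.05, which matches the 95% interval given.

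**The plan's own figure.** A two-sample t-test with difference 2, SD 2 and 20 per arm has power 86.9%, which agrees with the stated 87%. This does not identify the scale: power depends on difference/SD = 2/2 = 1.0, a ratio with no units.

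**Range under each reading of item 8.**

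| Item 8 coded | Maximum total | Item 8 share of range | Planned 2 points as share of range |
|---|---|---|---|
| 0 to 5, as printed | 7 × 1 + 5 = 12 | 5/12 = 41.7% | 2/12 = 16.7% |
| 0 to 4, one integer per option | 7 × 1 + 4 = 11 | 4/11 = 36.4% | 2/11 = 18.2% |
| maximum 1 | 7 × 1 + 1 = 8 | 1/8 = 12.5% | 2/8 = 25.0% |

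The category table leaves 8 − 7 = 1 point for item 8, so only the last row fits it.

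**Totals with no category.** The subtotal of items 1 to 7 takes 8 values (0 to 7). With item 8 at 0 to 5 there are 8 × 6 = 48 combinations, of which 1 + 2 + 3 + 4 = 10 exceed 8 (subtotals 4, 5, 6 and 7 respectively). With item 8 at 0 to 4 there are 8 × 5 = 40, of which 1 + 2 + 3 = 6 exceed 8. These are counts of cells, not probabilities.

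**Values per option.** Options A to E number 5 and the integers 0 to 5 number 6, so no one-to-one mapping exists. A cap of 1 alone would not settle it either: A = 0 with B to E = 1 and equal steps of 1/4 = 0.25 both reach a maximum of 1.

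**Effect on a change score.** A subject's change is the change in items 1 to 7 plus the change in item 8, and only the second term depends on the key. Assume only that A earns the lowest value and E the highest. A move from E to A then changes the total by −5, −4 or −1 under the three readings. The largest gap between keys for identical answers is 5 − 1 = 4 points.

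**Effect on the arm difference.** Two keys give arm differences that differ by the between-arm difference in their mean item 8 changes. That depends on how answers are distributed by arm and visit, which the documents do not give, so I do not put a figure on it.

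**The case against.** The best reply is that this is one bad cell. The Adherence assessment paragraph calls the scale eight-point and the category table ends at 8, so two places agree and only the item 8 entry is out of line. No passage states a total of 11 or 12. As evidence for a 0 to 8 total this stands. It does not correct the entry, however, and it does not say what each option is worth.

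Second, no planned analysis uses the High, Medium and Low categories, so totals without a category alter no estimate directly. That is true. The category table matters here as evidence that the points column conflicts with it; the harm is to the numeric score.

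Third, the 4-point gap is a worst case for one subject, and a share of the range is not a share of the variance. If most subjects choose A or B, item 8 may add little under any key. This also stands, and the figure should be read only as a bound.

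Fourth, nothing suggests that scoring would differ by arm or visit, and this is a pilot with no formal power analysis. One key applied throughout would keep the randomised comparison fair, but only once that key is fixed. The size and meaning of the difference would still depend on it, and the pilot attaches an effect size, interval and power to this score.

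Finally, the options sit in one table cell, so a lost layout of values per option cannot be fully excluded. Both tables otherwise read intact, and a lost layout would not bring a 0 to 5 range within a total of 8.

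**Conclusion.** The concern holds. As printed, the score behind the only primary outcome cannot be computed without choosing between two incompatible tables and then inventing values for item 8. The readings give maxima of 12, 11 or 8, with item 8 carrying 42%, 36% or 12.5% of the range, and the planned 2 points mean 16.7%, 18.2% or 25% of it. One subject's change can differ by up to 4 points between keys, assuming only that A scores lowest and E highest.

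The stated 87% power is reproduced and is not in question. No bias between arms is shown, and the documents do not allow the effect on the arm difference to be estimated. They favour a 0 to 8 total but cannot settle the correct scoring, which rests with the source instrument. This must be fixed before analysis because a stated rule for the primary outcome is wrong as written.

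**What to change.** Before analysis:

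1. Check the scoring of the instrument cited as reference 17 and reconcile the two tables in Appendix B1. The printed categories need item 8 capped at 1. If the source shows otherwise, correct the category table instead.
2. Print an explicit value for each of options A to E.
3. State which answer earns the point on each yes/no item. Item 5, "Did you take all your medicine yesterday", is worded the opposite way from the others, so a negative answer must earn its point if 0 is to mean High Adherence.
4. In the primary outcome paragraph of Section 10, give the total range, say that higher is worse, and state the order of subtraction.
5. Confirm that 2 ± 2 refers to that range.
6. Keep item-level answers so that both visits in both arms are scored with the same key.

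The cost is one appendix table and one or two sentences in Section 10, with no new visits or subjects. If item-level answers are kept, scores already recorded can be recomputed under the corrected key.

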Appendix B2: Memphis Medication Side Effect (MMSE) Scale

The following questions describe problems you might be having because of the transplant or the medicine you are taking. For each problem, you will be asked how frequently you experience it (the first row) and how troubling it is (the second row). Please answer every question.

	Not at all	Very little	Sometimes or Moderately troubling	Often or Very troubling	All the time or Extremely troubling
Enlarged gums					
Do you have this problem?					
How troubling is it?					
Increased hunger					
Do you have this problem?					
How troubling is it?					
Staying asleep					
Do you have this problem?					
How troubling is it?					
Weight gain					
Do you have this problem?					
How troubling is it?					
Increased hair growth					
Do you have this problem?					
How troubling is it?					
Infections					
Do you have this problem?					
How troubling is it?					
Trembling hands					
Do you have this problem?					
How troubling is it?					

High blood pressure					
---------------------	--------------------------	--------------------------	--------------------------	--------------------------	--------------------------

Do you have this problem?					
How troubling is it?					
Easy bruising					
Do you have this problem?					
How troubling is it?					
Loss of interest in sex					
Do you have this problem?					
How troubling is it?					
Sexual performance					
Do you have this problem?					
How troubling is it?					
Diabetes					
Do you have this problem?					
How troubling is it?					
Hair Loss					
Do you have this problem?					
How troubling is it?					

	Not at all	Very little	Sometimes or Moderately troubling	Often or Very troubling	All the time or Extremely troubling
Stomach pain					
Do you have this problem?					
How troubling is it?					
Nausea					
Do you have this problem?					
How troubling is it?					
Diarrhea					
Do you have this problem?					
How troubling is it?					

Vomiting					
Do you have this problem?					
How troubling is it?					
Stomach gas					
Do you have this problem?					
How troubling is it?					
Indigestion					
Do you have this problem?					
How troubling is it?					
Mood Changes					
Do you have this problem?					
How troubling is it?					
Depression					
Do you have this problem?					
How troubling is it?					
Nervousness or anxiety					
Do you have this problem?					
How troubling is it?					

Irritability					
Do you have this problem?					
How troubling is it?					
Anger					
Do you have this problem?					
How troubling is it?					
Keeping a positive attitude					
Do you have this problem?					
How troubling is it?					

	Not at all	Very little	Sometimes or Moderately troubling	Often or Very troubling	All the time or Extremely troubling
Feelings of uselessness					
Do you have this problem?					
How troubling is it?					
Being worried					
Do you have this problem?					
How troubling is it?					
Worthlessness					
Do you have this problem?					
How troubling is it?					
Hopelessness					
Do you have this problem?					
How troubling is it?					
Ability to concentrate					
Do you have this problem?					
How troubling is it?					
Completing daily errands					
Do you have this problem?					
How troubling is it?					
Participating in social activities					
Do you have this problem?					
How troubling is it?					
Doing housework					
Do you have this problem?					
How troubling is it?					

Doing yardwork					
Do you have this problem?					

How troubling is it?					
Performing my job					
Do you have this problem?					
How troubling is it?					
Participating in physical activities					
Do you have this problem?					
How troubling is it?					
Participating in leisure pastimes					
Do you have this problem?					
How troubling is it?					
Driving					
Do you have this problem?					
How troubling is it?					

	Not at all	Very little	Sometimes or Moderately troubling	Often or Very troubling	All the time or Extremely troubling
Being independent					
Do you have this problem?					
How troubling is it?					
Ability to travel on vacations					
Do you have this problem?					
How troubling is it?					
Reading					
Do you have this problem?					

How troubling is it?					
Decreased muscle strength					
Do you have this problem?					
How troubling is it?					
Climbing stairs					
Do you have this problem?					
How troubling is it?					
Walking					
Do you have this problem?					
How troubling is it?					
Bone pain					
Do you have this problem?					
How troubling is it?					
Stiff joints					
Do you have this problem?					
How troubling is it?					
Foot pain					
Do you have this problem?					
How troubling is it?					
Hip pain					
Do you have this problem?					
How troubling is it?					

Appendix B3: RAND 36-Item Health Survey 1.0 Questionnaire Items

SF-36 Resources

- [Terms and Conditions for Using the SF-36](#)
- [MOS 36-Item Short Form Survey Instrument \(SF-36\) \(English PDF\)](#)
- [MOS 36-Item Short Form Survey Instrument \(SF-36\) \(Arabic PDF\)](#)
- [Scoring Instructions for MOS 36-Item Short Form Survey Instrument \(SF-36\)](#)

Choose one option for each questionnaire item.

1. In general, would you say your health is:

- 1 - Excellent
- 2 - Very good
- 3 - Good
- 4 - Fair
- 5 - Poor

2. Compared to one year ago, how would you rate your health in general now?

- 1 - Much better now than one year ago
- 2 - Somewhat better now than one year ago
- 3 - About the same
- 4 - Somewhat worse now than one year ago
- 5 - Much worse now than one year ago

The following items are about activities you might do during a typical day. Does your health now limit you in these activities? If so, how much?

- | | Yes, limited
a lot | Yes, limited a
little | No, not
limited at all |
|--|-------------------------|--------------------------|---------------------------|
| 3. Vigorous activities, such as running, lifting heavy objects, participating in strenuous sports |  1 |  2 |  3 |
| 4. Moderate activities, such as moving a table, pushing a vacuum cleaner, bowling, or playing golf |  1 |  2 |  3 |
| 5. Lifting or carrying groceries |  1 |  2 |  3 |
| 6. Climbing several flights of stairs |  1 |  2 |  3 |
| 7. Climbing one flight of stairs |  1 |  2 |  3 |
| 8. Bending, kneeling, or stooping |  1 |  2 |  3 |
| 9. Walking more than a mile |  1 |  2 |  3 |
| 10. Walking several blocks |  1 |  2 |  3 |
| 11. Walking one block |  1 |  2 |  3 |
| 12. Bathing or dressing yourself |  1 |  2 |  3 |

During the past 4 weeks, have you had any of the following problems with your work or other regular daily activities as a result of your physical health?

- | | Yes | No |
|--|-------------------------|-------------------------|
| 13. Cut down the amount of time you spent on work or other activities |  1 |  2 |
| 14. Accomplished less than you would like |  1 |  2 |
| 15. Were limited in the kind of work or other activities |  1 |  2 |
| 16. Had difficulty performing the work or other activities (for example, it took extra effort) |  1 |  2 |

During the past 4 weeks, have you had any of the following problems with your work or other regular daily activities as a result of any emotional problems (such as feeling depressed or anxious)?

Yes No

17. Cut down the amount of time you spent on work or other activities 1 2

18. Accomplished less than you would like 1 2

19. Didn't do work or other activities as carefully as usual 1 2

20. During the past 4 weeks, to what extent has your physical health or emotional problems interfered with your normal social activities with family, friends, neighbors, or groups?

1 - Not at all

2 - Slightly

3 - Moderately

4 - Quite a bit

5 - Extremely

21. How much bodily pain have you had during the past 4 weeks?

1 - None

2 - Very mild

3 - Mild

4 - Moderate

5 - Severe

6 - Very severe

22. During the past 4 weeks, how much did pain interfere with your normal work (including both work outside the home and housework)?

1 - Not at all

2 - A little bit

- 3 - Moderately
- 4 - Quite a bit
- 5 - Extremely

These questions are about how you feel and how things have been with you during the past 4 weeks. For each question, please give the one answer that comes closest to the way you have been feeling.

How much of the time during the past 4 weeks...

- | | All of
the time | Most of
the time | A good bit
of the time | Some of
the time | A little of
the time | None of
the time |
|---|-------------------------|-------------------------|---------------------------|-------------------------|-------------------------|-------------------------|
| 23. Did you feel full of pep? |  1 |  2 |  3 |  4 |  5 |  6 |
| 24. Have you been a very nervous person? |  1 |  2 |  3 |  4 |  5 |  6 |
| 25. Have you felt so down in the dumps that nothing could cheer you up? |  1 |  2 |  3 |  4 |  5 |  6 |
| 26. Have you felt calm and peaceful? |  1 |  2 |  3 |  4 |  5 |  6 |
| 27. Did you have a lot of energy? |  1 |  2 |  3 |  4 |  5 |  6 |
| 28. Have you felt downhearted and blue? |  1 |  2 |  3 |  4 |  5 |  6 |
| 29. Did you feel worn out? |  1 |  2 |  3 |  4 |  5 |  6 |
| 30. Have you been a happy person? |  1 |  2 |  3 |  4 |  5 |  6 |
| 31. Did you feel tired? |  1 |  2 |  3 |  4 |  5 |  6 |

32. During the past 4 weeks, how much of the time has your physical health or emotional problems interfered with your social activities (like visiting with friends, relatives, etc.)?

- 1 - All of the time
- 2 - Most of the time

- 3 - Some of the time
- 4 - A little of the time
- 5 - None of the time

How TRUE or FALSE is each of the following statements for you.

	Definitely true	Mostly true	Don't know	Mostly false	Definitely false
33. I seem to get sick a little easier than other people	 1	 2	 3	 4	 5
34. I am as healthy as anybody I know	 1	 2	 3	 4	 5
35. I expect my health to get worse	 1	 2	 3	 4	 5
36. My health is excellent	 1	 2	 3	 4	 5

